### **6.10.3.3 Patient Reported Outcomes**

#### **Numerical Rating Scale (NRS)**

The NRS is a commonly used unidimensional scale which will be used as a measure of itch intensity. Subjects will complete the NRS at Baseline and Days 7, 14 and 28. A recall period of 24 hours will be used during which subjects will be asked to rate their average itch intensity (overall score) over those 24 hours and the itch intensity during the worst moment (peak score) of those 24 hours. For both of these questions, the subject will select a whole number from 0 to 10 corresponding to their itch intensity, where 0 is no itch and 10 is the worst itch imaginable.

Scores will be categorized mild, moderate and severe where mild is a score between 1 and 3 inclusive, moderate is a score between 4 and 6 inclusive and severe is a score between 7 and 10 inclusive. A score of 0 will be assigned a category of 'none' for the summaries and listings.

Descriptive statistics will be presented for both the overall score and the peak score observed values by dose group and visit. In addition, the number and percentage of subjects recording overall and peak scores within each severity band (none/mild/moderate/severe) will be presented by dose group and visit. Finally, the number and percentage of subjects recording a decrease from Baseline of  $\geq 4$  points in the overall and peak scores respectively will be presented by dose group for each post-Baseline visit, together with the number and percentage of subjects recording this decrease at any time post-Baseline. The denominator for all percentages will be the number of subjects with a non-missing score for the respective dose group and visit. The denominator for the summary of subjects recording a decrease of  $\geq 4$  points at any time post-Baseline will be the number of subjects with at least one non-missing post-Baseline score for the respective dose group and visit. The values used as the denominator will be included in the summary.

All NRS data will be listed including the observed score for each of the overall score and the peak score at each visit.

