The adult female mite burrows into the top layer of the skin (stratum corneum) where it lays eggs that hatch and develop into adults within approximately 2 weeks. The burrow is a pathognomonic sign of scabies but may not always be visible. Scabies is characterized by the development of an intensely itchy rash caused by an allergic reaction to the presence of mite antigens and feces in the skin. In a first infestation symptoms may take 4 to 6 weeks to manifest, but may appear after only a few days in second or subsequent infestations. The itch is often reported to be worse at night. The rash is papular in nature and typically, although not exclusively, occurs in locations that correspond to sites of predilection for infestation such as on the finger webs, wrists, flexures and genitalia. The mite burden in typical scabies infestations is thought to be 10 to 15, though hyperinfestation with hundreds of mites has been reported (Chosidow 2006, Currie and McCarthy 2014). Crusted scabies, the most severe form of the disease, occurs when the susceptible host is infected with millions of mites and hyperkeratotic skin crusts form, potentially due to an inability to immunologically control the infestation (Davis, et al. 2013).

A presumptive diagnosis of scabies is be made based on itch characteristics, clinical presentation of scabies lesions (including burrows and rash) in sites of predilection and suggestive history such as presence of a close contact with scabies or similar itch (Engelman, et al. 2018). A definitive diagnosis can be made using non-invasive microscopy (most commonly low-magnification dermoscopy) of suspected infestation sites or microscopic examination of skin scrapings to identify mites, eggs and/or fecal pellets (Engelman, et al. 2018). Reflectance confocal microscopy (RCM), a newer imaging technique using laser scanning to examine the top 300 to 500 µm of skin, can also be used to diagnose scabies (Cinotti, et al. 2015, Cinotti, et al. 2016, Micali, et al. 2016).

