### 2.2 Study Endpoints

The primary endpoints of the study are as follows:

- Efficacy will be determined by death of the mites, defined as the degradation (loss of internal and/or external anatomic structures) of the adult mite observed by reflectance confocal microscopy (RCM). Mites will be assessed at Hours 4, 8, 24, 48 and 72 and Days 7, 14 and 28 in not less than two lesions nominated pre-treatment.
- Safety will be assessed by the incidence and severity of adverse events (AEs), physical examinations, and measurement of vital signs up to and including Week 12, and laboratory safety parameters up to and including Day 28.

The secondary endpoints are the key exposure metrics for moxidectin including area under the concentration time curve (AUC) and maximum plasma concentration ( $C_{max}$ ), which will be determined by non-compartmental analysis of moxidectin pharmacokinetic parameters or other methods as appropriate, assessed up to and including Day 28.

The exploratory endpoints are:

- At Hours 4, 8, 24, 48 and 72 and Days 7, 14 and 28, using assessment by RCM of burrows selected pre-treatment:
  - Changes in adult mite motility (peristalsis and/or movement) over at least 30 seconds of observation;
  - Presence, number, morphology and motility of juvenile scabies mites;
  - Presence of eggs and scybala in burrows.
- Presence and total number of mites and burrows assessed visually at Days 7, 14 and 28.
- Changes in assessment of clinician-reported scabies symptomology, including extent of symptoms on body regions assessed by the number of anatomically-defined regions affected, number of lesions and severity grading of excoriations and erythema.
- Changes in patient reported outcomes, measured by Numerical Rating Scale, 5-D Itch Scale and Dermatology Life Quality Index.
- Clinical cure rates at Days 7, 14 and 28. Clinical cure is defined as resolution of all scabies signs and symptoms present at Baseline, no new scabies signs and symptoms and no evidence of mites by dermoscopy.

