#### **5-D Itch Scale**

The 5-D Itch Scale measures five dimensions (duration, degree, direction, disability and distribution) of the impact of itching on the subject. The questionnaire consists of five items relating directly to each of the five dimensions. Subjects will complete the 5-D Itch Scale at Baseline and Days 7, 14 and 28. A recall period of one week will be used.

Questions 1 to 3 will be answered using a five-point Likert scale. These questions are scored according to the value selected by the subject i.e. the lowest duration, degree or direction response is scored a 1 and the highest duration, degree or direction is scored a 5.

Question 4 is subdivided into four further subcategories of sleep, leisure/social, housework/errands and work/school also answered using a five-point Likert scale. The highest scoring response to these four sub-questions is taken as the score for question 4. The subcategories of leisure/social, housework/errands and work/school can be answered with an additional category of N/A, however as the highest score of the four subcategories is used for this question, and N/A is not an option for sleep, the overall score remains in the range of 1 to 5.

Question 5 requires the subject to indicate the areas in which they have experienced itching in the previous one week period. The number of body parts selected is then attributed the following scores: 0-2 body parts = 1, 3-5 body parts = 2, 6-10 body parts = 3, 11-13 body parts = 4 and 14-16 body parts = 5.

The overall score is calculated as the summation of the scores of Questions 1 to 3, the highest score of Question 4 and the collated score of Question 5. The overall score ranges from 5 to 25 where higher scores indicate an increased itch related impact.

Overall scores will be categorized mild, moderate and severe where mild is a score between 5 and 11 inclusive, moderate is a score between 12 and 17 inclusive and severe is a score between 18 and 25 inclusive.

Descriptive statistics will be presented for the overall 5-D Itch Scale score observed values over time, as well as summaries of subjects by severity band and subjects with a decrease from Baseline of  $\geq 4$  points as described for the NRS scores above.

All 5-D Itch Scale data will be listed including the observed score for each question and sub-question and the overall score at each visit.

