### **Dermatology Life Quality Index (DLQI)**

The DLQI is a 10-item questionnaire to assess health-related quality of life. Subjects will complete the DLQI at Baseline and Days 7, 14 and 28.

For questions 1 to 6 and 8 to 10, the following responses are required: "not at all," "a little," "a lot," or "very much". The scoring for each of these questions is as follows: Very much = 3, a lot/quite a lot = 2, a little = 1, not at all = 0, not relevant = 0, question unanswered = 0.

For question 7, if the answer is yes = 3, if no and no further information provided = 0, if no and the further question is asked then the responses are as follows: A lot = 2; a little = 1; Not at all, N/A or incomplete = 0.

The overall DLQI score is calculated as the total score over all items and ranges from 0 to 30 where higher scores indicate greater health-related quality of life impairment.

The overall DLQI score will also be categorized as mild, moderate and severe where mild is a score between 0 and 5 inclusive, moderate is a score between 6 and 10 inclusive and severe is a score between 11 and 30 inclusive.

Descriptive statistics will be presented for the overall DLQI score observed values over time, as well as summaries of subjects by severity band and subjects with a decrease from Baseline of  $\geq 4$  points as described for the NRS scores above.

All DLQI data will be listed including the observed score for each question as well as the overall score at each visit.

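### The 4-point-decrease tables for itch and quality of life count subjects who start too low to fall by 4 points, so an able-to-respond percentage and change from Baseline should be added beside them

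*SAP*

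**What the plan says.** SAP 2.2 names the exploratory endpoint as "Changes in patient reported outcomes, measured by Numerical Rating Scale, 5-D Itch Scale and Dermatology Life Quality Index". SAP 6.10.3.3 plans three kinds of table for the NRS: descriptive statistics of observed scores by visit, severity bands by visit, and "the number and percentage of subjects recording a decrease from Baseline of" 4 points or more. The last is given at each post-Baseline visit and at any time post-Baseline.

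The per-visit rule is "The denominator for all percentages will be the number of subjects with a non-missing score for the respective dose group and visit". For the any-time row the denominator "will be the number of subjects with at least one non-missing post-Baseline score for the respective dose group and visit". The denominators are to be displayed. The 5-D and DLQI sections adopt the banding and 4-point summaries by reference to the NRS text.

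On the NRS, "the subject will select a whole number from 0 to 10 corresponding to their itch intensity". The 5-D total runs from 5 to 25 and the DLQI total from 0 to 30. The NRS has a separate band for a score of 0. On the 5-D, "mild is a score between 5 and 11 inclusive"; on the DLQI, "mild is a score between 0 and 5 inclusive". All scores are listed by subject and visit.

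Protocol 8.2 and 8.3 set no minimum itch or DLQI score.

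**The concern.** A responder definition based on an absolute fall needs room to fall. Where the starting score is within 3 points of the scale minimum, the outcome is fixed as non-response before dosing. Entry is confirmed by live mites on RCM rather than by symptoms, and Protocol 5.1 allows for infestation ahead of symptoms: "In a first infestation symptoms may take 4 to 6 weeks to manifest". The DLQI scoring also gives 0 to unanswered and not-relevant items, which can lower a Baseline total.

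Arms have about 6 subjects, and neither Protocol 10.1 nor SAP 4 balances allocation on baseline itch. The observed response rate therefore reflects how many subjects in an arm had room to improve as well as how many improved.

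The responder count is also the only tabulated within-subject change for an endpoint that is defined as change. By contrast, SAP 6.14.2 plans change from Baseline for laboratory values. What is at stake is how well the itch and quality-of-life tables can be read across doses.

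**Working it through.** The plan states no expected response rate or Baseline distribution for these scores, so there is no plan figure to reproduce. The inputs are the threshold (4 points), the scale minima (0, 5, 0) and the denominators, all from SAP 6.10.3.3, and about 6 subjects per arm, from SAP 3. Two quantities are assumed: q, the share of subjects starting too low to respond, and r, the response rate among the others.

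**Step 1. Who cannot respond.** A fall of 4 is impossible when Baseline minus the scale minimum is below 4:

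- NRS: 0–3. This is exactly the NRS none and mild bands combined.
- 5-D: 5–8. The mild band is 5–11, so it does not isolate them.
- DLQI: 0–3. The mild band is 0–5, so it does not isolate them.

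A subject with no Baseline score has no computable change but is in the denominator once a visit score exists. The questionnaires are scheduled only once before dosing, so no Screening score is planned that could replace a missing one.

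**Step 2. Ceiling in an arm of 6.** With k such subjects the highest attainable rate is (6 − k)/6: 83% for k = 1, 67% for k = 2, 50% for k = 3. Each subject costs 1/6, about 17 points. Protocol 5.4.3 allows initial cohorts of about 3 to 6; in an arm of 3, one such subject gives a ceiling of 2/3 = 67%.

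**Step 3. Dilution.** Expected displayed rate = r(1 − q). With r = 80% and q = 20%: 0.80 × 0.80 = 64%.

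**Step 4. Chance imbalance.** Let the number of such subjects in each of three arms be an independent Binomial(6, q) count, with p(k) the probability of k.

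- P(at least one in an arm) = 1 − (1 − q)^6. For q = 20%: 1 − 0.8^6 = 0.738.
- P(largest minus smallest is at most 1) = Σ over k of [(p(k) + p(k+1))³ − p(k+1)³]. For q = 20% the first three p(k) are 0.2621, 0.3932 and 0.2458, and the sum is 0.502. So P(difference of 2 or more) = 1 − 0.502 = 0.498.

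| Assumed q | P(at least one in an arm of 6) | P(three arms differ by 2 or more) | Mean largest-to-smallest gap in attainable rate | Displayed rate if r = 80% |
|---|---|---|---|---|
| 0% | 0 | 0 | 0 | 80% |
| 5% | 0.265 | 0.090 | 11 points | 76% |
| 10% | 0.469 | 0.256 | 18 points | 72% |
| 20% | 0.738 | 0.498 | 26 points | 64% |
| 30% | 0.882 | 0.601 | 31 points | 56% |
| 40% | 0.953 | 0.645 | 33 points | 48% |

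**Step 5. Effect of the added row.** Among subjects able to respond the expected rate is r whatever q is. For example, if two of six could not respond and the other four all did, the plan's row shows 4/6 = 67% and the added row shows 4/4 = 100%.

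**The case against.** The strongest reply is that the size depends entirely on q, which may be small, at least for the NRS. The Protocol synopsis says subjects are identified from a presumptive clinical diagnosis. Protocol 5.1 bases that diagnosis partly on itch and describes the rash as intensely itchy. People who are infested but not yet symptomatic are less likely to arrive by that route. This stands. It does not exclude low scores, particularly on the DLQI, but it rules out presenting any one value of q as expected.

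Second, the percentage of all assessed subjects with a 4-point fall is a legitimate description. It is low only against a different quantity, the rate among subjects able to respond. Restricting the denominator outright would drop subjects from arms of 6. It would also leave a dependence on Baseline: a subject at NRS 4 must reach 0, while one at 10 need only reach 6. This stands too, and it argues for adding a row rather than replacing one.

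Third, the decision impact is low. SAP 6.10.3 makes these endpoints exploratory and descriptive. Protocol 15.2 and SAP 6.10.1.4 frame dose choice on parasitological effect with acceptable safety. SAP 5.1 has the Steering Committee guided by mite mortality or time to death, safety and possibly pharmacokinetics. The point about missing Baseline scores is also minor, since the questionnaires are scheduled before dosing.

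A reader might further infer that change cannot be seen elsewhere, or that full resolution cannot be told from mild disease on the 5-D and DLQI. The documents do not support either. Observed scores by visit give the mean change when the same subjects contribute, the descriptive statistics include the minimum, and every score is listed. With about 6 subjects per arm, a 5-D of 5 or a DLQI of 0 is visible there.

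**Conclusion.** The point holds conditionally. It is certain that the denominators include subjects who cannot meet the criterion, on all three scales, and that eligibility does not keep such subjects out. If they enrol, the displayed rate is r(1 − q) instead of r, and arms of about 6 can differ appreciably in their attainable rate by chance. The imbalance figures rest on independent arms of exactly 6 and on a value of q that the documents do not supply; q may also differ between the scales.

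A reader might conclude that the response rates are biased down and do differ between arms, or that dose selection is compromised. Neither follows: the first needs a Baseline distribution that the documents do not give, and the second conflicts with the stated dose-choice criteria.

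This is a cheap improvement to exploratory descriptive tables. It is better made before the Day 28 unblinding: SAP 6.10.3 allows post-hoc analyses, but a denominator chosen then would be chosen with the dose results in view.

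**What to change.** In SAP 6.10.3.3 and the table shells:

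1. Keep the all-subject 4-point percentage as planned.
2. Beside it, add the percentage among subjects with a non-missing visit score and a Baseline score of at least 4 (NRS overall and peak, each on its own Baseline), at least 9 (5-D) or at least 4 (DLQI), and show that N. For the any-time row, require at least one post-Baseline score instead.
3. Show by dose group the number of subjects below that Baseline limit and the number with no Baseline score.
4. Add change from Baseline to the descriptive statistics for all three instruments.

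A separate none band for a 5-D total of 5 and a DLQI total of 0 is an optional presentation change.

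The cost is SAP wording and shell edits, with no new data. The downside is extra table rows and a smaller N in the added row, which is why the all-subject row should stay.

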#### **5-D Itch Scale**

The 5-D Itch Scale measures five dimensions (duration, degree, direction, disability and distribution) of the impact of itching on the subject. The questionnaire consists of five items relating directly to each of the five dimensions. Subjects will complete the 5-D Itch Scale at Baseline and Days 7, 14 and 28. A recall period of one week will be used.

Questions 1 to 3 will be answered using a five-point Likert scale. These questions are scored according to the value selected by the subject i.e. the lowest duration, degree or direction response is scored a 1 and the highest duration, degree or direction is scored a 5.

Question 4 is subdivided into four further subcategories of sleep, leisure/social, housework/errands and work/school also answered using a five-point Likert scale. The highest scoring response to these four sub-questions is taken as the score for question 4. The subcategories of leisure/social, housework/errands and work/school can be answered with an additional category of N/A, however as the highest score of the four subcategories is used for this question, and N/A is not an option for sleep, the overall score remains in the range of 1 to 5.

Question 5 requires the subject to indicate the areas in which they have experienced itching in the previous one week period. The number of body parts selected is then attributed the following scores: 0-2 body parts = 1, 3-5 body parts = 2, 6-10 body parts = 3, 11-13 body parts = 4 and 14-16 body parts = 5.

The overall score is calculated as the summation of the scores of Questions 1 to 3, the highest score of Question 4 and the collated score of Question 5. The overall score ranges from 5 to 25 where higher scores indicate an increased itch related impact.

Overall scores will be categorized mild, moderate and severe where mild is a score between 5 and 11 inclusive, moderate is a score between 12 and 17 inclusive and severe is a score between 18 and 25 inclusive.

Descriptive statistics will be presented for the overall 5-D Itch Scale score observed values over time, as well as summaries of subjects by severity band and subjects with a decrease from Baseline of  $\geq 4$  points as described for the NRS scores above.

All 5-D Itch Scale data will be listed including the observed score for each question and sub-question and the overall score at each visit.

### **Dermatology Life Quality Index (DLQI)**

The DLQI is a 10-item questionnaire to assess health-related quality of life. Subjects will complete the DLQI at Baseline and Days 7, 14 and 28.

For questions 1 to 6 and 8 to 10, the following responses are required: "not at all," "a little," "a lot," or "very much". The scoring for each of these questions is as follows: Very much = 3, a lot/quite a lot = 2, a little = 1, not at all = 0, not relevant = 0, question unanswered = 0.

For question 7, if the answer is yes = 3, if no and no further information provided = 0, if no and the further question is asked then the responses are as follows: A lot = 2; a little = 1; Not at all, N/A or incomplete = 0.

The overall DLQI score is calculated as the total score over all items and ranges from 0 to 30 where higher scores indicate greater health-related quality of life impairment.

The overall DLQI score will also be categorized as mild, moderate and severe where mild is a score between 0 and 5 inclusive, moderate is a score between 6 and 10 inclusive and severe is a score between 11 and 30 inclusive.

Descriptive statistics will be presented for the overall DLQI score observed values over time, as well as summaries of subjects by severity band and subjects with a decrease from Baseline of  $\geq 4$  points as described for the NRS scores above.

All DLQI data will be listed including the observed score for each question as well as the overall score at each visit.

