### **6.2 General Derivations**

This section provides details of general derivations. Derivations specific to a parameter of interest are detailed within the specific SAP sections.

- **Definition of study day**

Throughout this SAP any references to 'Day XX' refer to the pre-specified visits defined in the protocol (where the study drug administration visit is Day 0).

Data listings by visit will additionally present the duration from the administration of study drug in days, referred to as 'Study Day XX'. Study Day will be calculated relative to the date of administration of study drug in whole days. Thus, assessments completed on the day of study drug administration ('Day 0' visit) will be assigned a Study Day value of 1.

- **Definition of Baseline**

Baseline is defined as the last non-missing value (including scheduled and unscheduled assessments) prior to the subject receiving study drug.

- **Incomplete dates**

For calculation purposes, incomplete dates will be completed using a worst case approach. For example, assuming the earliest or latest possible date given all available information to ensure a worst case applies for each respective case. Further details are provided in the relevant sections as required.

- **Non-numeric values**

In the case where a variable is recorded as " $> x$ ", " $\geq x$ ", " $< x$ " or " $\leq x$ ", then for analysis purposes a value of  $x$  will be taken. Where a range of values is quoted, the midpoint of the range will be taken.

- **Site pooling for statistical analyses**

No analysis by center or country will be performed due to the small sample size of the study. Subjects from all centers will be pooled for summaries and analyses.

- **Methods for handling withdrawals and missing data**

In general, data will not be imputed unless otherwise stated in relevant sections.

- **Definition of planned dose and actual dose received**

Planned dose of study drug is defined as the dose group to which the subject was randomized and will be determined by the randomization list. Actual dose received is defined as the actual dose of study drug received regardless of randomized dose group. This will be determined once the blind has been broken using details provided by MDGH and/or captured on the electronic Case Report Form (eCRF) regarding actual doses received by subjects.

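### Unanswered DLQI items score 0, the best value, with no limit on blanks and no rule for when the total is missing, so two or more blanks can create a 4-point decrease in an unchanged subject

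*SAP*

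**What the plan says.** The DLQI subsection of SAP 6.10.3.3 states "The DLQI is a 10-item questionnaire to assess health-related quality of life". Questions 1 to 6 and 8 to 10 are scored "Very much = 3, a lot/quite a lot = 2, a little = 1", with 0 for the lowest answer, and "not relevant = 0, question unanswered = 0". For question 7, a yes scores 3. After a no, the follow-up scores 2 or 1, and otherwise "Not at all, N/A or incomplete = 0"; a no with nothing further also scores 0. A wholly blank question 7 is not mentioned.

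The total is the sum over all items and "ranges from 0 to 30 where higher scores indicate greater health-related quality of life impairment". The bands are mild 0 to 5, moderate 6 to 10 and severe 11 to 30.

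The total feeds three outputs: descriptive statistics, severity bands, and the number of subjects whose score falls by at least 4 points from Baseline. By reference to the NRS paragraph of the same section, that count is made at each visit and also for any visit after Baseline, among subjects with a non-missing score.

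The SAP gives the DLQI no maximum number of blanks, no proration and no statement of when a partly completed form has a missing total. Protocol 15.7.8 places the scoring of these instruments in the SAP. Protocol 9.4.8.2 refers to the study reference manual for questionnaire details; that manual is not among the documents.

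**The concern.** A blank carries no information about impairment, yet it receives the same score as a clear statement of no impairment. In the total the two cannot be told apart. Because the rule has no limit, a form that is mostly empty still yields a low, non-missing total, enters the denominator and is likely to fall in the mild band.

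Blanks after Baseline look like improvement. Blanks at Baseline make the starting point look better than it was and can conceal improvement. The any-visit count adds exposure: one incomplete form among Days 7, 14 and 28 is enough to count a subject. With about 6 subjects per dose group, one such form visibly changes the group's percentage.

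**Working it through.** **Inputs.** From SAP 6.10.3.3: 10 items, maximum 3 each, blank = 0, the three bands and the 4-point decrease. From SAP 3: about 6 subjects per dose group. The item profiles in step 4 and the numbers of blanks are assumptions, because the documents give no skip rate.

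**1. The plan's own figure.** 10 × 0 = 0 and 10 × 3 = 30, so the stated range of 0 to 30 reproduces.

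**2. Artificial fall.** For an unchanged subject with a complete Baseline form, the fall equals the sum of the true scores of the items left blank, so it is at most 3m for m blanks.

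| Blanks m | Largest fall 3m | Can reach 4? |
|---|---|---|
| 1 | 3 | no |
| 2 | 6 | yes |
| 3 | 9 | yes |

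With equal item scores, reaching 4 takes four blanks if each is truly 1, and two if each is truly 2 or 3. A blank that is truly 0 has no effect. If only one item is answered, the total is at most 3, which is in the mild band.

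**3. Illustration.** True score 12 (severe) at both visits, with two items truly scored 2 left blank later: 12 − 2 × 2 = 8. The fall is 4 and the band changes to moderate. In a group of 6, 1/6 = 16.7 percentage points.

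**4. How often the threshold is met.** For assumed unchanged profiles, every possible set of m blank items was enumerated with equal weight. The share giving a fall of at least 4 is:

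| Assumed item scores (total) | m = 1 | m = 2 | m = 3 | m = 4 |
|---|---|---|---|---|
| all 2 (20) | 0% | 100% | 100% | 100% |
| five 2s, five 1s (15) | 0% | 22% | 92% | 100% |
| 3, 3, 2, 2, 1, 1 and four 0s (12) | 0% | 22% | 50% | 74% |
| all 1 (10) | 0% | 0% | 0% | 100% |

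The band is more sensitive than the 4-point count. In the total-12 profile a single blank moves the subject from severe to moderate in 4 of 10 cases, namely when the item is truly 2 or 3.

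**5. Blanks at Baseline.** With a true fall of 5 and two Baseline items truly scored 2 left blank, the observed fall is 5 − 4 = 1, and the 4-point decrease is missed.

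**6. Effect of allowing one blank only.** The artificial fall is then at most 3, below 4, so skipping alone cannot make an unchanged subject meet the criterion. This needs an unanswered question 7 follow-up to count as a blank. Otherwise one blank item (up to 3) plus that follow-up (up to 2) could still remove 5 points.

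**The case against.** The best defence is that the rule is explicit, prespecified and of small consequence. The questionnaires are administered at clinic visits, and Protocol 16.2.4 requires unavailable information to be indicated in the CRF. The reference manual may contain completeness checks. DLQI is one of three patient-reported measures in an exploratory, descriptive endpoint and is not among the criteria listed to guide the steering committee. Item scores are listed, and SAP 6.1 and 6.10.3 allow post-hoc work. All of this limits the weight of the point. It does not say when a DLQI total is missing, and it is unclear whether a listing of observed scores would distinguish a blank from a true 0.

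Some stronger readings are tempting but not supported:

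- **Conflict with SAP 6.2.** A reader might infer one, but 6.2 says "In general, data will not be imputed unless otherwise stated in relevant sections", and the DLQI text is such a statement.
- **Contrast with the primary endpoint.** A reader might infer that the SAP imputes toward the worse case there and the better case here. SAP 6.10.1.3 does treat an unsure morphology response as live and ignores deaths after rescue medication. It also treats a lesion no longer visible as a dead mite and ignores a live status after a dead one. There is no uniform direction to contrast with.
- **Likely skipping.** A reader might suppose that certain questions, or translated forms, invite blanks. The documents describe neither the DLQI item content nor the language of the forms.

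**Conclusion.** The scoring rule, followed as written, can give a wrong result: two or more blanks after Baseline can alone produce a 4-point decrease, and even one can produce a better severity band. The largest distortion is 3 points per blank.

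The 16.7-point figure is the effect of one such subject in a group of 6. It is not an expected bias, because the skip rate is unknown and the example was chosen to land on the threshold. Nor is there a one-way bias toward benefit: a blank can only lower or leave unchanged the score at its own visit, but the change from Baseline can be distorted in either direction. The explicit blank rule covers nine items; for question 7 only the follow-up is covered.

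No inferential result and no stated dose decision rests on the DLQI. This is a minor point, worth making because the correction is simple.

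**What to change.** In the DLQI part of SAP 6.10.3.3:

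- Score a blank as 0 only when a single item is unanswered. Count question 7 as unanswered if it is wholly blank or if its follow-up is left unanswered after a no.
- With two or more unanswered items, set the DLQI total, severity band and 4-point decrease status to missing for that visit. If the visit is Baseline, the decrease status is missing at every later visit.
- Keep the not-relevant answer at 0.
- In the listing, show unanswered items as blank and give their number.

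The cost is a short SAP edit and a small programming change. A few totals may become missing and denominators will shift slightly: one subject is 1/6 = 16.7% of a group of 6 but 1/5 = 20% if one form is set to missing. Two effects remain. A single blank can still cross a band, for example 11 − 3 = 8. It can also lift a true fall of 1 to the threshold (1 + 3 = 4). The number of blanks in the listing lets a reader see where this could have happened.
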